 BMI > 30 is exclusionary. Body weight will be measured at screening and end of study (V7) for all subjects. Drastic weight loss or gain may skew assessments of "before" and "after" photos.

 Required for women of childbearing potential

 Pregnancy test not required at V6 if no BOTOX touch-up is needed.

 New subject diary only administered at touch-up if injection occurred. Collect completed diary at the next scheduled visit.

 FACE-Q Scales include Satisfaction with Facial Appearance Scale, Expectations Scale (baseline only), Aging Appraisal, Psychological Function Scale, Social Function Scale, and Satisfaction with Skin Questionnaire.

 FACE-Q Expectations subscale will not be collected at End of Study.

 If HArmonyCa injections are not to be administered to a subject, the subject will begin at Day 1 with V3 study activities (i.e., Juvéderm fillers).

 HArmonyCa touch-up, if required. If not required, proceed with V3 study activities.

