2.2 Study Design Overview

This Phase 4 study is a prospective, interventional, multicenter, combination medical device and drug post marketing study. Each subject will be in the study for up to approximately 5 months and act as his/her own control. All products will be used as per their license only. The investigators will perform all treatments and evaluations.

The study is planned to enroll 60 subjects consecutively at approximately 7 study sites in Brazil. Recruitment will also target men, who are typically under-represented in aesthetic studies.

All subjects will sign an informed consent form (ICF) and begin the study at the screening visit (V0). Subjects following screening (V0) will enter the study and receive an initial treatment of HArmonyCa Lidocaine at Visit 1 (V1), followed by Juvéderm fillers at Visit 3 (V3), and BOTOX at Visit 5 (V5) as indicated in the study design diagram ([Figure 1](#)). If the decision is made to not treat with HArmonyCa Lidocaine, the subject may begin with Juvéderm fillers at V1. As indicated in the diagram, touch-ups of HArmonyCa at Visit 2 (V2), Juvéderm at Visit 5 (V5), and BOTOX at Visit 6 (V6) are optional. If a touch-up of HArmonyCa (V2) is not performed, the subject may advance in the study timeline to the next study visit procedures. If a touch-up of BOTOX is not performed, the subject will return on schedule for Visit 7 (V7). A

subject not receiving Juvéderm touch-up would continue with BOTOX treatment (and all study procedures) outlined for V5. To reduce the number of subject visits, V0 can be combined with the initial treatment visit (V1), if judged by the investigator to be appropriate and acceptable for the subject. End of study is the last clinical visit an enrolled subject has in this study, V7 (after approximately 5 months of treatment). Subjects who discontinue prematurely will be asked to return for the last clinical visit for end-of-study data collection. Identical study procedures will not be repeated where the visits are combined. The schedule of activities is shown in [Table 1](#).

Figure 1. Study Design

[figure not shown]

Table 2. Schedule of Activities (SOA)

Study Visit	V0 ¹	V1	V2	V3	V4	V5	V6 ²	V7 ³
Visit window	Screening	Day 1	Day 30	Day 60	Day 90	Day 120	Day 135	Day 150
	(Day -14 to Day -1)	N/A	(30 ± 7 days after V1)	(30 ± 7 days after V2)	(30 ± 7 days after V3)	(30 ± 7 days after V4)	(15 ± 7 days after V5)	(15 ± 7 days after V6)
STUDY TREATMENTS								

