- ¹¹ FACE-Q Scales include Satisfaction with Facial Appearance Scale, Expectations Scale (baseline only), Aging Appraisal, Psychological Function Scale, Social Function Scale, and Satisfaction with Skin Questionnaire.
- ¹² FACE-Q Expectations subscale will not be collected at End of Study.
- ¹³ If HArmonyCa injections are not to be administered to a subject, the subject will begin at Day 1 with V3 study activities (i.e., Juvéderm fillers).
- ¹⁴ HArmonyCa touch-up, if required. If not required, proceed with V3 study activities.

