5.0 Subject Disposition and Treatment Disposition

The number and percentage of subjects who are in the mITT Population, Evaluable Population, and Safety Population will be summarized by treatment group (HArmonyCA, Non-HArmonyCA), gender (male, female), and overall, for all eligible subjects (subjects who signed the informed consent and met all eligibility criteria). Screen failure subjects and the reasons for screen failure will also be summarized by overall, for all screened subjects.

A listing of screen failure subjects, inclusion/exclusion criteria assessment and all analysis populations will be presented for all screened subjects.

The number and percentage of subjects who complete the study and who discontinue from the study will be presented by treatment group, gender, and overall, for all screened subjects. The number and percentage of subjects who complete all treatments (HArmonyCA, JUVÉDERM, and BOTOX) and discontinue from any of the treatments (HArmonyCA, JUVÉDERM, and BOTOX) as collected on the CRF will also be presented by treatment group, gender, and overall, for all screened subjects. The primary reason for study discontinuation and treatment discontinuation will be presented as collected on the eCRF. Reasons for discontinuation include:

- Adverse Event
- Lost to Follow-Up
- Pregnancy
- Withdrawal by Subject
- Study Terminated by Sponsor
- Physician Decision
- Protocol Deviation
- Other

A listing of study disposition and treatment disposition will be provided for the Safety Population.

The duration in study (days) will be summarized by treatment group, gender, and overall, for the Safety Population. It is calculated as (Last Assessment Date in the Study – First Assessment Date in the Study) + 1.

A listing of study visits will be provided for the Safety Population.

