9.0 Safety Analyses

9.1 General Considerations

- All safety analyses will be conducted by treatment group, gender, and overall, for the Safety Population.

- Adverse events (AEs) will be coded using the medical dictionary for Regulatory Activities (MedDRA). The actual version of the MedDRA coding dictionary will be noted in the statistical outputs and clinical study report.

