9.2.1 Treatment-Emergent Adverse Events

Treatment-emergent adverse event (TEAE) is defined as any AE with the onset on or after the date (and time, if known) of the first study treatment. A TEAE will be considered a treatment-

emergent serious adverse event (TESAE) if it is a TEAE that additionally meets any SAE criterion.

All AEs will be included in a listing. Only TEAEs will be included for summaries, unless otherwise specified. Subjects with any TEAEs, TESAEs, severe TEAEs, TEAEs related to study treatment, TEAEs related to study procedure, TEAES related to device, TEAEs leading to study discontinuation, TEAEs leading to death, TESAEs related to study treatment, TESAEs related to study procedure, TESAEs related to device, TESAEs leading to study discontinuation, and TESAEs leading to death will be summarized.

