9.2.2 Adverse Event Overview

Overall summaries of TEAEs will include:

- The number and percentage of subjects with any TEAE
- The number and percentage of subjects with any TESAE
- The number and percentage of subjects with any severe TEAE
- The number and percentage of subjects with any TEAE related to JUVÉDERM VOLITE
- The number and percentage of subjects with any TEAE related to JUVÉDERM VOLBELLA
- The number and percentage of subjects with any TEAE related to JUVÉDERM VOLIFT
- The number and percentage of subjects with any TEAE related to JUVÉDERM VOLUMA
- The number and percentage of subjects with any TEAE related to JUVÉDERM VOLUX
- The number and percentage of subjects with any TEAE related to BOTOX cosmetic
- The number and percentage of subjects with any TEAE related to study procedure
- The number and percentage of subjects with any TEAE related to device
- The number and percentage of subjects with any TEAE leading to study discontinuation

- The number and percentage of subjects with any TEAE leading to death
- The number and percentage of subjects with any TESAE related to JUVÉDERM VOLITE
- The number and percentage of subjects with any TESAE related to JUVÉDERM VOLBELLA
- The number and percentage of subjects with any TESAE related to JUVÉDERM VOLIFT
- The number and percentage of subjects with any TESAE related to JUVÉDERM VOLUMA
- The number and percentage of subjects with any TESAE related to JUVÉDERM VOLUX
- The number and percentage of subjects with any TESAE related to BOTOX cosmetic
- The number and percentage of subjects with any TESAE related to study procedure
- The number and percentage of subjects with any TESAE related to device
- The number and percentage of subjects with any TESAE leading to study discontinuation
- The number and percentage of subjects with any TESAE leading to death
 - Before BOTOX Treatment
 - On or After BOTOX Treatment

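### All-cause adverse-event percentages by HArmonyCA group set a nominal 150 or 120 days of observation against 90 days

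*SAP*

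**What the plan says.** **Groups and metric.** SAP 9.1: "All safety analyses will be conducted by treatment group, gender, and overall, for the Safety Population". SAP 5.0 defines the groups when it says that population counts "will be summarized by treatment group (HArmonyCA, Non-HArmonyCA), gender (male, female), and overall". The overview in SAP 9.2.2 consists of lines of the form "The number and percentage of subjects with any TEAE", and the tables by system organ class and preferred term (SOC/PT) also give numbers and percentages of subjects. No adverse-event table uses person-time, a common window or a time-to-event method.

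**Counting window.** A TEAE is "any AE with the onset on or after the date (and time, if known) of the first study treatment" (SAP 9.2.1). Collection of adverse events ends at V7 (SAP 3.3, Protocol 4.3).

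**Visit timing.** Protocol Table 6.1 and the schedule in SAP 2.2 time each visit from the one before. Two footnotes shorten the path:

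- Footnote 13, no HArmonyCa: "If HArmonyCa injections are not to be administered to a subject, the subject will begin at Day 1 with V3 study activities".
- Footnote 14, HArmonyCa without touch-up at V2: "HArmonyCa touch-up, if required. If not required, proceed with V3 study activities".

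Protocol 6.2.3 also times V3 from the previous treatment. Yet SAP 2.2 and Protocol 11.1 place the end of study at "V7 (after approximately 5 months of treatment"), while SAP 2.2 elsewhere gives about 5 months as an upper limit for each subject.

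**What partly addresses this.** SAP 5.0 summarises duration in study by treatment group, as a separate table. SAP 9.5 uses a fixed 30-day diary after each filler treatment and summarises injection site reactions by visit.

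**The concern.** The two groups leave the study at different times because of the visit rules themselves, not because of dropout. A longer-observed group accumulates more first events even when the daily risk is the same, so a crude percentage makes the shorter-observed group look safer.

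This matters because the addition of HArmonyCa is the stated reason for protocol Version 2 (Appendix 14). The treatment-related rows in SAP 9.2 name the five Juvéderm products and BOTOX but not HArmonyCa, so a reader looking for its adverse events will turn to the all-cause rows by treatment group. Those are the rows in which product effect and observation time cannot be told apart. A duration table elsewhere in the report shows that follow-up differs, but gives no way to compare the groups over equal time.

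**Working it through.** **1. Inputs.** Intervals from Protocol Table 6.1: V1–V2, V2–V3, V3–V4 and V4–V5, 30 ± 7 days each; V5–V6, 15 + 7 days; V6–V7, 15 ± 7 days. Path rules from footnotes 13 and 14.

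**2. The plan's own figure.** Full path: 4 × 30 + 15 + 15 = 150 days, which matches the scheduled Day 150 for V7.

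**3. The other paths.** Footnote 14 removes one 30-day interval, and footnote 13 removes two.

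| Path | Sum of intervals | Nominal days, first treatment to V7 | Window extremes |
|---|---|---|---|
| HArmonyCa with touch-up | 4 × 30 + 15 + 15 | 150 | 115–192 |
| HArmonyCa, no touch-up | 3 × 30 + 15 + 15 | 120 | 92–155 |
| No HArmonyCa | 2 × 30 + 15 + 15 | 90 | 69–118 |

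Ratios to the last row: 150/90 = 1.67 and 120/90 = 1.33. The HArmonyCA column pools the first two paths in an unknown proportion.

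**4. Where the extra time lies.**

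- First HArmonyCa to first Juvéderm: 60, 30 or 0 days.
- First Juvéderm to V7: 30 + 30 + 15 + 15 = 90 days on every path.
- First BOTOX to V7: 15 + 15 = 30 days on every path.

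**5. Which rows are affected.** The overview in SAP 9.2.2 has 23 rows. Twelve are tied to Juvéderm or BOTOX: five Juvéderm products plus BOTOX, for TEAEs and again for serious TEAEs (TESAEs). Such an event cannot precede the product, so these rows have about equal windows. The other 11 have unequal windows: any TEAE, any TESAE, severe, and the procedure-related, device-related, discontinuation and death rows for TEAEs and TESAEs. The same holds for the SOC/PT tables not tied to Juvéderm or BOTOX.

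**6. Illustrative size.** The documents give no adverse-event rate, so the 90-day incidence p is an assumption. With the same constant hazard in everyone, the proportion with an event by day t is 1 − (1 − p)^(t/90). For p = 30%: 1 − 0.7^(120/90) = 37.8% and 1 − 0.7^(150/90) = 44.8%.

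| Assumed at 90 days | At 120 days | At 150 days | Ratio at 120 | Ratio at 150 |
|---|---|---|---|---|
| 5% | 6.6% | 8.2% | 1.32 | 1.64 |
| 10% | 13.1% | 16.1% | 1.31 | 1.61 |
| 30% | 37.8% | 44.8% | 1.26 | 1.49 |
| 50% | 60.3% | 68.5% | 1.21 | 1.37 |
| 60% | 70.5% | 78.3% | 1.18 | 1.30 |

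**7. Check on an exposure-adjusted rate.** For all-cause events under the p = 30% model, first events per 100 subject-days at risk, counted from first treatment, come to about 0.40 on all three paths (simulated 0.397, 0.396, 0.396), so the artefact disappears.

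For a Juvéderm-related event the same denominator fails. Suppose 30% have one in the 90 days after first Juvéderm on every path. Mean time at risk in that window is 0.30 / 0.00396 per day = 75.7 days. Counting from first treatment adds 30 or 60 days, and the rates become:

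- no HArmonyCa: 0.30/75.7 = 0.396 per 100 days;
- HArmonyCa, no touch-up: 0.30/105.7 = 0.284;
- HArmonyCa with touch-up: 0.30/135.7 = 0.221.

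That is a false deficit of 28% to 44% in the HArmonyCA column.

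**The case against.** **Most of the safety output is sound.** A reader might infer that every safety table by group is distorted. The documents do not support that: 12 of the 23 overview rows and the diary reactions have about equal windows. This stands and limits the point to the other rows.

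**HArmonyCa safety is visible elsewhere.** A reader might also infer that the group columns are the only view of it. They are not. Reactions by visit (SAP 9.5) cover the HArmonyCa sessions, device deficiencies are shown by device type (SAP 9.8), and all adverse events are listed. This stands too.

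**The constant-hazard gap may not be an artefact.** The 30-day diaries suggest that reactions are expected to follow injections. If so, part of any excess comes from the added HArmonyCa session(s) and is real. The largest gap also needs every HArmonyCa subject to have a touch-up. This stands: the figures illustrate and do not predict. It does not rescue the crude percentage, which cannot separate the two sources.

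**No comparison is planned.** The study is single-arm, HArmonyCa use is not randomised, no between-group safety test exists, and SAP 5.0 already discloses duration by group. So no type I error is at stake, and confounding would remain after any adjustment for time. But the SAP does print the columns side by side, and a separate duration table does not put them on equal time.

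**Other details soften the contrast.** Some text says that subjects may advance, so actual times will vary. Reporting of serious events runs 30 days past exit on every path (Protocol 10.5.2), which gives 180 or 150 against 120 days where those are counted, ratios of 1.5 and 1.25. The line "On or After BOTOX Treatment" and its pre-BOTOX counterpart are printed under deaths, and whether they apply to the whole overview cannot be settled from the text. If they do, the pre-BOTOX periods are still about 120 or 90 against 60 days.

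**Conclusion.** The point holds for the all-cause, severe, procedure-related, device-related, discontinuation and death rows and for the matching SOC/PT tables. There, nominal observation is 1.33 or 1.67 times as long in the HArmonyCA group, and a crude difference mixes product effect with time.

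The time ratio follows from the visit rules, taken at nominal intervals. Its effect on the percentages is unknown. Under constant hazard and an assumed 30% by Day 90, identical risk would produce a gap of about 8 points (37.8 − 30) to 15 points (44.8 − 30). Over assumed incidences of 5% to 60%, the risk ratio from time alone would be 1.18–1.32 at 120 days and 1.30–1.64 at 150 days. If events cluster after injections, some of that gap would be a real effect of the regimen.

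This is an inexpensive improvement to descriptive output. It does not touch the primary analysis.

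**What to change.** In SAP 9.2, keep the crude percentages. For the affected rows and tables, add by treatment group:

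1. TEAE incidence from the first Juvéderm session to V7, nominally 90 days on all paths.
2. TEAE incidence in the HArmonyCa stage, from first HArmonyCa to before first Juvéderm, shown separately for the HArmonyCA group.

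If an exposure-adjusted rate is also wanted, limit it to the all-cause rows with time at risk from first treatment, or start the clock for each product-related row at the first injection of that product. One denominator for all rows would introduce the opposite bias.

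Reconcile the statement in SAP 2.2 and Protocol 11.1 that V7 follows about 5 months of treatment with footnotes 13 and 14 and with the wording that treats 5 months as an upper limit.

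The cost is SAP wording and a few table columns from dates already collected. The output grows slightly, and the comparison stays descriptive and non-randomised.

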9.2 Adverse Events

Adverse events (AEs) will be summarized and presented using primary MedDRA System Organ Classes (SOCs) and preferred terms (PTs).

An AE will be considered a JUVÉDERM injection related AE if it has a reasonable possibility (Possible, Probable, or Causal relationship) that the JUVÉDERM injections caused the event. The JUVÉDERM injections include JUVÉDERM VOLITE, JUVÉDERM VOLBELLA, JUVÉDERM VOLIFT, JUVÉDERM VOLUMA, and JUVÉDERM VOLUX.

An AE will be considered a BOTOX related AE if it has a reasonable possibility (Reasonable Possibility) that the BOTOX cosmetic caused the event.

An AE will be considered a study procedure related AE if it has a reasonable possibility (Possible, Probable, or Causal relationship) that the study procedure caused the event.

An AE will be considered a device related AE if it is related to a device malfunction/deficiency.

If the causal relationship to the study treatment/device/procedure is missing for an AE that occurred on or after the date of the first study treatment, then a causal relationship will be imputed for analysis. The imputed values for relationship to study treatment/device/procedure will be used for the incidence summary; the actual values will be presented in data listings.

If severity is missing for an AE that occurred before the date of first study treatment, then a severity of mild will be imputed for analysis. If the severity is missing for an AE that occurred on or after the date of the first study treatment, then a severity of severe will be imputed. The imputed values for severity will be used for the incidence summary; the actual values will be presented in data listings.

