## 10.7.2 Relationship to Study Product

A determination will be made, by the investigator, of the relationship, if any, between an AE and any study product, anesthesia employed, the study device, or the injection procedure, as applicable, using the guidelines presented in **Table 10.2**.

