**Table 10.2 Guidelines for Determining the Relationship Between Adverse Event and the Study Product**

Highly Probable	This causal relationship is assigned if the AE starts a reasonable time after the administration of study product, stops/improves when the study product is stopped, and could reasonably be explained by known characteristics of the study product.
Probable	This causal relationship is assigned when the AE starts a reasonable time after the administration of study product, stops/improves when the study product is stopped, and could not be reasonably explained by known characteristics of the subject's clinical state.
Possible	This causal relationship is assigned when the AE starts a reasonable time after the administration of study product but could be produced by the subject's clinical state or other modes of therapy administered to the subject.
Not Related	This causal relationship is assigned when the time association or the subject's clinical state is such that the study product was not likely to have had an association with the observed AE.

Abbreviations: AE = adverse event.

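### The causality levels that make an adverse event Juvéderm-, BOTOX- or procedure-related in SAP 9.2 do not match the protocol's causality scale, and no mapping is given

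*SAP*

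**What the plan says.** **Protocol.** Section 10.7.2 asks the investigator for a judgement "of the relationship, if any, between an AE and any study product, anesthesia employed, the study device, or the injection procedure, as applicable", using Table 10.2. One scale therefore serves the drug, the fillers, the device and the procedure. Its four levels are:

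- "Highly Probable", listed first: timing fits, the event stops or improves when the product is stopped, and known properties of the product could explain it.
- Probable: timing and improvement as above, and the event "could not be reasonably explained by known characteristics of the subject's clinical state".
- Possible: timing fits, "but could be produced by the subject's clinical state or other modes of therapy administered to the subject".
- Not Related.

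**SAP.** Section 9.2 defines relatedness separately for each cause:

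- Juvéderm: an event counts "if it has a reasonable possibility (Possible, Probable, or Causal relationship) that the JUVÉDERM injections caused the event".
- Study procedure: the same three labels.
- BOTOX: an event counts "if it has a reasonable possibility (Reasonable Possibility) that the BOTOX cosmetic caused the event".
- Device: the event must be tied to a malfunction or deficiency. No causality level is used.

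The same section says that an event on or after first treatment with no recorded causality is imputed as causal for the incidence summaries. SAP 1.0 sends the reader to Appendix C for departures from the protocol's analyses. None of its five rows concerns causality.

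**The concern.** The related-event results rest on a label list that is not the list the protocol tells investigators to use. The strongest protocol level is missing from the SAP's Juvéderm and procedure lists. The SAP's strongest label, Causal relationship, does not exist in the protocol, and the only BOTOX label is not a protocol level either.

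At stake are the rows for events and serious events related to each Juvéderm product, to BOTOX and to the procedure in the SAP's Adverse Event Overview, and the matching tables by system organ class and preferred term. In a single-arm, open-label study of combined products, these rows are where the plan attributes harm to a product or to the procedure. A reader must be able to tell what related means in them.

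**Working it through.** There is no stated figure to reproduce and no sample-size formula applies. The check compares labels.

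| Rating | In Protocol Table 10.2 | Counts for Juvéderm (SAP 9.2) | Counts for procedure (SAP 9.2) | Counts for BOTOX (SAP 9.2) |
|---|---|---|---|---|
| Highly Probable | yes | not listed | not listed | not listed |
| Probable | yes | yes | yes | not listed |
| Possible | yes | yes | yes | not listed |
| Not Related | yes | no | no | no |
| Causal relationship | no | yes | yes | not listed |
| Reasonable Possibility | no | not listed as a level | not listed as a level | yes |

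**Overlap.** Of the three protocol levels that express some relationship, two are listed for Juvéderm and the procedure (3 − 1 = 2), and none for BOTOX (3 − 3 = 0). Highly Probable is listed in 0 of the 3 definitions that use causality levels. The fourth definition, device-related, uses no level and is outside the comparison.

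**Is a mapping given elsewhere?** Appendix C has none. The SAP points to its Statistical Programming Plan for questionnaire scoring and for the Hodges-Lehmann interval, but section 9.2 does not point there for causality.

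**What follows depends on what the eCRF collected:**

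1. *Ratings collected on Table 10.2, SAP labels applied literally.* The overview counts subjects, not events. A subject leaves a Juvéderm or procedure row only if every one of that subject's otherwise qualifying ratings is Highly Probable; one Possible or Probable rating keeps the subject in. Without the ratings, the loss in a given row can lie anywhere between no subjects and all of them. In the BOTOX row no recorded rating qualifies. Meanwhile an event with no rating is imputed as causal, so a missing judgement would count as related while the strongest recorded judgement would not.
2. *Ratings collected with the SAP's labels.* No event is lost. But Table 10.2 was then not the scale applied, and BOTOX was judged on a different scale from the fillers although the protocol sets one for all. Neither fact is recorded.

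**The case against.** The strongest reply is that the test in SAP 9.2 is whether there is a reasonable possibility of causation, with the labels only in parentheses. A Highly Probable event meets that test in ordinary language, and a programmer would probably equate the level with Causal relationship. The literal reading also gives the implausible result that no BOTOX event could ever be rated related. In addition, one label set for device and procedure and another for the drug looks like separate eCRF fields, in which case the SAP simply describes the data.

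This is plausible, and it makes the loss of events conditional. It does not remove the mismatch. The parentheses are what turn a general phrase into a rule that can be programmed, and no mapping to the protocol's levels is written. The eCRF and the programming plan are not among the documents, so the guess about the fields cannot be confirmed.

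It can also be said that Table 10.2 is titled as guidelines, that Protocol 11.5 sets no cut-off for related, and that Appendix C is meant for changed analyses. That is fair as far as it goes. But Protocol 11.5 does plan a summary by relationship to drugs, devices and procedures, and a different set of levels changes what that summary means. No other place in the SAP records it.

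Safeguards also stand. All adverse events are listed. Treatment-emergent, severe and serious events are summarised whatever their causality. Diary-reported injection site reactions are tabulated without a causality filter. Events would not be hidden; only their attribution is at risk.

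**Conclusion.** The mismatch is certain on the text and should be corrected. It concerns the three SAP 9.2 definitions that use causality levels: Juvéderm, BOTOX and study procedure. Its consequence is conditional. With Table 10.2 ratings and literal labels, Highly Probable events drop out of the Juvéderm and procedure rows and no rating qualifies for BOTOX. With the SAP's labels on the eCRF, the defect is an unrecorded change of scale.

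Three stronger conclusions are tempting, and the documents do not support them:

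- *Treatment-related harm is understated.* This holds only in the first case, and the documents do not show which case applies.
- *The understatement can be put at some percentage.* The share of events rated Highly Probable is not given, and a share of events would not convert directly to the subject counts in the tables.
- *Every related-event row is affected.* The device-related rows rest on malfunction or deficiency and do not depend on the list.

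**What to change.** In SAP 9.2, state the causality levels actually collected for each study product and for the procedure, and map every level to related or not related, with the top level (Highly Probable or Causal relationship) counted as related. If Table 10.2 was used, related means Highly Probable, Probable or Possible, for BOTOX as for the fillers. If the eCRF used other labels, give the correspondence with Table 10.2, reconcile the two documents, and record the change of scale in Appendix C. Simply substituting the Table 10.2 labels without checking the eCRF could create a new mismatch.

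Because the statement should cover each study product, it should include HArmonyCa, for which SAP 9.2 currently gives no related-event definition.

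The cost is a few words in SAP 9.2, a short mapping, and a row in Appendix C if the scale changed. No new data are needed. The downside for the sponsor is that related-event counts may become slightly less favourable.
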